5. STATISTICAL HYPOTHESES FOR STUDY OBJECTIVES

5.1. Primary Hypotheses

All primary hypotheses must be met in order to satisfy the primary objective of this study.

1. The Test lens will be non-inferior to the Control lens with respect to Distance Monocular logMAR Visual Acuity at the two-week follow-up evaluation under both lighting conditions (Bright illumination low contrast and dim illumination high contrast). A non-inferiority margin of 0.05 logMAR will be used.

2. The Test lens will be non-inferior to the Control lens with respect to the percentage of eyes with Grade 3 or higher Slit Lamp Findings (Biomicroscopy) across all follow-up visits (scheduled and unscheduled). A non-inferiority odds ratio margin of 2 will be used.
3. The proportion of eyes with acceptable fit will be greater than 90% across all visits (scheduled and unscheduled) for all subjects wearing the Test lens.
4. The Test lens will be non-inferior to the Control lens with respect to CLUE Overall Comfort at the two-week follow-up evaluation. A non-inferiority margin of -5 points will be used.
5. The Test lens will be non-inferior to the Control lens with respect to Vision satisfaction in bright lighting at the two-week follow-up evaluation. A non-inferiority cumulative odds ratio margin of 0.67 will be used.

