8.4. Sample Size Justification

This study was designed and powered to show non-inferiority of the Test lens compared to the Control lens with respect to logMAR Visual Acuity, Slit Lamp Findings (Grade 3 or higher), CLUE comfort, handling and overall quality of vision. It was assumed there was no difference between the Test and Control lens with respect to visual acuity and slit lamp findings. Based on data from 3 historical studies, it was assumed there was a 5-, 3- and 4-point difference between the Test and Control lenses with respect to CLUE comfort, handling and overall quality of vision, respectively.

In addition to the endpoints mentioned above this study was also powered to demonstrate non-inferiority of the Test lens relative to the Control lens with respect to vision satisfaction in bright lighting, overall quality of vision indoors and the proportion of eyes with acceptable fitting while the Test lens is significantly superior to 90%. Unless otherwise specified, the sample size was calculated to achieve a minimum statistical power of 80% and a type I error of 5%.

A total of 5 historical studies were utilized in the sample size calculation. Table 5 displays the studies, their corresponding study design and the number of subjects enrolled and completed per-protocol.

Table 5: Historical Studies Included in Sample Size Calculation

Study	Study Design	Endpoints Collected	No. Enrolled	No. Completed Per-Protocol
████████	2X3 Crossover	CLUE, SLF, Lens Fit	135	132
████████	2X3 Crossover	CLUE, Visual Acuity (logMAR), SLF, Lens Fit	133	121
████████	2X3 Crossover	CLUE, SLF, Lens Fit	92	78
████████	Single-Arm	SLF, Lens Fit	54	48
████████	Single-Arm	SLF, Lens Fit	56	41

Table 6: Descriptive Summary of CLUE Scores by Domain Pooled Across Historical Studies

████████ – 2-Week Follow-up Evaluation

CLUE Domain [Mean(SD) ¹]	Test	Control
Comfort	66.46 (22.20)	61.19 (24.20)
Handling	69.61 (19.18)	66.79 (20.01)
Overall Quality of Vision	64.15 (18.83)	60.33 (22.29)

¹SD = Standard Deviation

Table 7: Descriptive Summary of Visual Acuity (logMAR) - █ – 2-Week Follow-up Evaluation

Visual Acuity High Illumination High Contrast [Mean(SD) ¹]	Test	Control
	-0.0928 (0.08253)	-0.0726 (0.08011)

¹SD = Standard Deviation

Table 8: Descriptive Summary of Mechanical Lens Fitting Pooled Across all Historical Studies

Any Unacceptable Lens Fit ¹ [n(%)]	Test n (%)	Control n (%)
Fitting Evaluation	0 (0.0)	0 (0.0)
2-Week Follow-up	1 (0.05)	0 (0.0)

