¹The percent of any unacceptable fit is calculated using Total Unique eyes as a denominator

Table 9: Descriptive Summary of Slit Lamp Findings Pooled Across all Historical Studies

SLF Grade 2	Test n (%)	Control n (%)
Corneal Edema	0 (0.0)	0 (0.0)
Conjunctival Injection	55 (8.09)	59 (21.85)
Tarsal Abnormalities	51 (5.93)	24 (8.89)
Corneal Neovascularization	0 (0.0)	0 (0.0)
Corneal Staining	2 (0.29)	0 (0.0)
Other Findings	0 (0.0)	0 (0.0)
Total Eyes (N)	680	270
Any SLF Grade 2 ²	108 (15.8)	83 (33.74)
Any SLF Grade 3+	0 (0.0)	0 (0.0)
Total Unique Eyes	680	270

Total Unique Subjects	340	135
-----------------------	-----	-----

%= nx100/N; SD=Standard Deviation

¹All SLF reported for this study are combined for the purposes of summarizing

² The percent (%) of Any Grade 2 is calculated using the Total Unique Eyes as the denominator

Table 10: Descriptive Summary of Individual Items from [REDACTED] – 2-Week Follow-up

Questionnaire Item/ Response	Test	Control
Vision Satisfaction in Bright Light [n(%)]		
Strongly Agree	65 (35.9)	35 (19.2)
Agree	89 (49.2)	95 (52.2)
Neither Agree Nor Disagree	24 (9.92)	17 (9.3)
Disagree	13 (7.2)	29 (15.9)
Strongly Disagree	0 (0.0)	6 (3.3)
Overall Quality of Vision Indoors [n (%)]		
Excellent	100 (55.2)	80 (44.0)
Very Good	55 (30.4)	62 (34.1)
Good	23 (12.7)	30 (16.5)
Fair	3 (1.7)	7 (3.9)
Poor	0 (0.0)	3 (1.65)

CLUE Comfort

Sample size calculation for CLUE comfort was carried out using an approximation of the power of an F-test derived from the non-centrality parameter calculated from the observed F statistic of a linear model³.

Model details:

CLUE comfort was analyzed using a linear mixed model. Lens type was included as the only fixed effect. An unstructured (UN) covariance matrix was used to model the correlation between measurements on the same subject across study periods. Below is the variance-covariance matrix used in the CLUE Comfort model.

$$\sum_{comfort} \begin{pmatrix} 397.18 & 142.48 & 144.55 \\ 142.48 & 411.89 & 210.90 \\ 144.55 & 210.90 & 370.83 \end{pmatrix}$$

Visual Performance (logMAR)

Sample size calculation for visual performance (logMAR) was carried out using an approximation of the power of an F-test derived from the non-centrality parameter calculated from the observed F statistic of a linear model³.

Model details:

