8.5. Statistical Significance Level

All planned analysis will be conducted with an overall type I error rate of 5%. There will be neither adjustment for multiple tests nor adjustment for multiplicity of endpoints. Unless otherwise specified, all statistical tests will be 2-sided.

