Non-inferiority will be declared if the lower bound of the 2-sided 95% credible interval of the difference between the Test lens and the Control lens is greater than -5, i.e., $P(\beta_1 > -5) \geq 0.975$.

Vision Satisfaction in Bright Lighting

Vision satisfaction in bright lighting will be analyzed using a Bayesian multinomial model for ordinal data. The regression model will include sequence of lens wear, lens type, period and first order carryover effect. Clinical site and subject nested within clinical site will be included as random effects. Other subject characteristics such as age, gender, race and iris category will be included when appropriate.

The Model:

Let $y_{ijklm} = (y_{ijklm1}, y_{ijklm2}, y_{ijklm3}, y_{ijklm4}, y_{ijklm5})$ denote the rating for the m^{th} subject, from the l^{th} site, assigned to the i^{th} study lens in the j^{th} period using the k^{th} sequence. Possible values of y_{ijklm} are 1 if the subject rating of vision satisfaction in bright lighting are X and 0 otherwise (x=1 for Strongly Agree and X=5 for Strongly Disagree, respectively). The likelihood is constructed as follows:

$$y_{ijklm} \sim \text{Multinomial}(P_{ijklm1}, P_{ijklm2}, P_{ijklm3}, P_{ijklm4}, P_{ijklm5})$$

$$P_{ijklm1} = \gamma_{ijklm1}$$

$$P_{ijklmX} = \gamma_{ijklmX} - \gamma_{ijklm(X-1)} \quad 2 \leq n \leq 4$$

$$P_{ijklm5} = 1 - \sum_{x=1..4} P_{ijklmX}$$

$$\text{Logit}(\gamma_{ijklmX}) = \theta_n + \beta_1 \text{Lens}_{i[j,k]} + \beta_2 \text{Period}_{j1} + \beta_3 \text{Period}_{j2} + \beta_4 \text{Sequence}_k + \beta_5 \text{Carry}_{i[j,k]} + \gamma_l + \delta_{m(l)}$$

Where θ_n is the intercept for levels n=1,2,3,4, $P_{ijklm1} = \text{Pr}(\gamma_{ijklm1} = 1)$ with respect to the vision satisfaction in bright lighting item. We assume the random subject effects are independent identically distributed (i.i.d) as $\delta_{m(l)} \sim N(0, \sigma_{\text{subject}}^2)$ for subject m nested within clinical site l and

the random clinical site effects are i.i.d as $\gamma_l \sim N(0, \sigma_{site}^2)$ for $i=1,2$ (lens), $j=1, 2, 3$ (Period) $k=1, 2$ (Sequence) $l=1, \dots, 6$ (Site) $m=1, \dots, n_l$ (subject/site).

In this model, the lens I will be determined by the period j and sequence k , therefore i is denoted as a function of j and k . We define $Lens_i=0$ for the Control lens and $Lens_i=1$ for the Test lens. The cumulative odds ratio for having higher rating can be written as $OR=e^{\beta_1}$.

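### The stated CLUE comfort power of 87% at 30 completers holds only at a one-sided 5% level; under the one-sided 2.5% rule that decides the endpoint it is about 75–78%

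*SAP*

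**What the plan says.** SAP section 8.4 sets the general target: "the sample size was calculated to achieve a minimum statistical power of 80% and a type I error of 5" per cent. It does not say whether that error is one- or two-sided. Section 8.5 adds "Unless otherwise specified, all statistical tests will be 2-sided".

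For the CLUE domains, section 8.4 relies on three historical studies: "it was assumed there was a 5-, 3- and 4-point difference between the Test and Control lenses" for comfort, handling and overall quality of vision respectively. Table 6 shows that the Test lens had the higher mean in each domain. The comfort calculation is described as an "approximation of the power of an F-test derived from the non-centrality parameter", with lens type the only fixed effect and a printed 3×3 unstructured covariance. Table 11 gives 30 completers and 87% power. Protocol section 14.2 has the same inputs, and its Table 10 the same result.

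The hypothesis in SAP section 5.1 is "The Test lens will be non-inferior to the Control lens with respect to CLUE Overall Comfort at the two-week follow-up evaluation", with a margin of −5 points. The rule in section 11.1 is "Non-inferiority will be declared if the lower bound of the 2-sided 95% credible interval of the difference between the Test lens and the Control lens" exceeds −5, written there as a posterior probability of at least 0.975 that β1 is above −5.

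**The concern.** With vague priors, a rule that needs 97.5% posterior probability behaves like a one-sided 2.5% test. A power figure computed at one-sided 5% describes a looser test than the one that will be run, and so overstates the chance of success at the quoted sample size.

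Comfort is a primary endpoint, and section 5.1 requires every primary hypothesis to be met. Table 11 also appears to mix error levels. In the slit lamp simulation, section 8.4 compares the upper limit of a 95% confidence interval with the margin, which is one-sided 2.5% if the interval is the usual two-sided one. The power column then cannot be read on one footing, and nothing in the SAP says so.

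**Working it through.** **Inputs.** Covariance Σ from SAP 8.4: diagonal 397.18, 411.89, 370.83; off-diagonals 142.48 (periods 1,2), 144.55 (1,3), 210.90 (2,3). Sequences Test/Control/Control and Control/Test/Test, allocated 1:1, so 15 subjects each at n = 30. Assumed difference +5 and margin −5, a distance of 10. The observed difference in Table 6 is 66.46 − 61.19 = 5.27, a distance of 10.27. The SAP does not give the denominator degrees of freedom, so 29, 59, 88 and the normal limit are used as a range.

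**Standard error of the lens effect.** The information matrix is 15 × (X1′Σ⁻¹X1 + X2′Σ⁻¹X2), with an intercept and a lens column coded (1,0,0) in one sequence and (0,1,1) in the other. Its elements are 0.12483 (intercept), 0.06241 (cross term) and 0.10616 (lens).

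- Variance = 1 / (0.10616 − 0.06241² / 0.12483) = 1 / 0.07495 = 13.34.
- SE = 3.653.

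**Power.** The normal form is Φ(distance/SE − z). The F form is the upper tail of a noncentral F(1, df) with non-centrality (distance/SE)², here 100 / 13.34 = 7.50 for a distance of 10. The F critical value is taken at 10% for one-sided 5% and at 5% for one-sided 2.5%.

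- One-sided 5%, normal: 10/3.653 − 1.645 = 1.093, giving 86.3%.
- One-sided 2.5%, normal: 10/3.653 − 1.960 = 0.778, giving 78.2%.

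| df | 1-sided 5%, distance 10 | 1-sided 5%, distance 10.27 | 1-sided 2.5%, distance 10 | 1-sided 2.5%, distance 10.27 |
|---|---|---|---|---|
| 29 | 84.8% | 86.4% | 75.4% | 77.6% |
| 59 | 85.6% | 87.2% | 76.8% | 79.0% |
| 88 | 85.8% | 87.4% | 77.3% | 79.4% |
| normal | 86.3% | 87.8% | 78.2% | 80.3% |

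The 87% is recovered in the one-sided 5% columns, most closely with the observed difference. No one-sided 2.5% entry reaches it. Reading 30 as the number per sequence (60 in total) does not explain it either, since that gives about 97% or more.

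**With the further design terms.** Adding period, sequence and carryover raises the SE to 3.703. Power at n = 30, one-sided 2.5% and distance 10 becomes 74.2–77.1%.

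**Completers needed at one-sided 2.5%, lens only, distance 10.** The normal form is n = 30 × 13.34 × ((1.960 + z)/10)².

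- For 80% (z = 0.842): 31.4, so 32. The t-based answer is 34.
- For 87% (z = 1.126): 38.1, so 39. The t-based answer is 41.

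**At the planned 105 completers.** SE = 3.653 × √(30/105) = 1.952. Then 10/1.952 − 1.960 = 3.16, giving 99.9%.

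**The two sources of SD.** The square roots of the printed diagonal are 19.9, 20.3 and 19.3. Table 6 gives 22.20 (Test) and 24.20 (Control). As an assumption, take the larger SD in every period with the correlations implied by the printed matrix (0.35, 0.38, 0.54). Power at 105 is then 98.6% (t-based, lens only), or 98.4% with the further terms.

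**The case against.** The strongest reply is that nothing in the design depends on this row. Section 8.4 says the sample size was driven by overall quality of vision indoors, at 95 subjects. At 105 completers comfort has ample power under the assumed benefit. That stands, and it makes this a correction to a stated figure. A reader might infer that the trial is underpowered for comfort; under the SAP's own assumptions it is not.

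A reader might also infer that 87% contradicts the printed covariance. It does not. The matrix and the stated 5% error, read as one-sided, give the figure to within rounding. Only the error level departs from the decision rule.

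The gap between the matrix SDs and Table 6 could suggest that the covariance is wrong and that power at 30 is nearer 58–69%. The documents do not establish this. The printed diagonal agrees with the CLUE scale's nominal SD of 20. Table 6 pools raw scores across studies and may include between-study spread. The lower range also borrows its correlations from the matrix in question. What remains is an unexplained difference.

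It is also tempting to say that the 81% for handling and 82% for vision carry the same fault. No covariance is printed for either domain, so those rows can be neither confirmed nor refuted.

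Finally, the SAP model adjusts for baseline comfort and includes a random site effect, which the recalculation omits. Baseline adjustment could raise power. The documents give no figure from which to judge by how much, and the SAP's own power calculation did not use it.

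**Conclusion.** The comfort row is computed at a looser level than the rule it is meant to describe. At the assumed 5-point benefit, the power matching the decision rule at 30 completers is about 75–78%, or 74–77% with period, sequence and carryover. That is roughly 9–12 points below the stated 87% with lens only (87 − 78.2 and 87 − 75.4), and under the SAP's 80% minimum. If the observed 5.27 points is used instead, the range is 77.6–80.3%, so the 80% threshold is reached only at the normal limit.

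This rests on the printed covariance, equal allocation, and treating the 97.5% posterior rule with vague priors as a one-sided 2.5% test. That one-sided 5% was used is an inference from the reproduction; the SAP does not state it.

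The conclusion about 105 completers depends on the assumed advantage. If the lenses are truly equal, the distance is 5 and 5/1.952 − 1.960 = 0.60, giving about 73%. Across the t-based and fuller-model variants it is 71–73%. This is context for reading the row and is not an error in the plan.

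**What to change.** In SAP section 8.4 and protocol section 14.2:

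1. State the sidedness of the 5% error, consistent with section 8.5 and the 0.975 rule.
2. Restate the comfort row of SAP Table 11 and protocol Table 10 at one-sided 2.5%. Either give about 75–78% at 30 completers, or give the number that delivers the stated power (about 39–41 for 87%, 32–34 for 80%).
3. Check the handling and vision rows of SAP Table 12 and protocol Table 11 at the same level, restate them if needed, and print the covariances used.
4. Say which historical data the comfort covariance was fitted to, and why its SDs of 19.3–20.3 are below the 22.2–24.2 in Table 6.

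It would be useful, though optional, to report comfort power at 105 completers under both the assumed benefit and no difference. The cost is a short recalculation and revised text; enrolment, conduct and the decision rule do not change.

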The non-inferiority odds ratio margin of 2 corresponds to no more than a 5% difference between the Test and Control lenses assuming the Control reference rate does not exceed 10%.

Individual Questionnaire Items

Overall quality of vision outdoors and vision satisfaction in bright lighting sample size estimates were calculated using historical data from [REDACTED]. One-thousand boot strap

samples were simulated based on the historical data. For each replicated sample a generalized linear mixed model was used with a multinomial distribution and the cumulative logit as the link function. Lens wear sequence, lens type, period and first order carryover effect were included in the model as fixed effects. A variance component (VC) covariance structure was used to model the measurements between subjects across study periods.

The non-inferiority cumulative odds ratio margin of 0.67 corresponds to no more than a 10% difference between the Test and Control lenses assuming there is no difference between study lenses.

Table 10: Sample Size Estimates and Power Calculations for Primary Endpoints

Endpoint	Number per Subjects to Complete	Power
Distance Monocular Visual Acuity (logMAR)	4	80%
SLFs (Grade 3 or Higher)	50	80%
Acceptable lens Fit	65	80%
CLUE Comfort	30	87%
Vision Satisfaction in Bright Lighting	48	81%

Table 11: Sample Size Estimates and Power Calculations for Secondary Endpoints

Endpoint	Number per Subjects to Complete	Power
CLUE Handling	30	81%
CLUE Overall Quality of Vision	30	82%
Overall Quality of Vision Indoors	95	81%

As indicated in Table 10 and 11 above, the sample size chosen for this study was primary driven by overall quality of vision indoors. The plan is to enroll 120 eligible subjects with a target of 105 subjects to complete the study. During the enrollment period, the subject dropout rate will be closely monitored, if an unexpectedly high dropout rate is observed, then the targeted total enrollment number may be increased accordingly to ensure that a minimum of 105 subjects complete the study.

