3. STUDY DESIGN

3.1. Overview

This study is a randomized, 4-visit, partially subject-masked, 2x3 bilateral crossover, dispensing trial. Approximately 120 subjects will be screened and enrolled to ensure that at least 105 subjects complete.

The study begins with an initial visit (Visit 1). If a subject is found to meet all eligibility criteria, they will be randomized to one of two lens wear sequences (Test/Control/Control or Control/Test/Test).

If the subject is dispensed their first study lenses at the initial visit then 3 additional visits will be conducted. Their first follow-up visit will occur at approximately 2-weeks after initial dispensing (Visit 2). At visit 2, subjects will be dispensed their next lens as specified per the randomization. Subjects' follow-up for their second lens will occur approximately 2-weeks after visit 2 (Visit 3). Subjects will be dispensed their last study lens (per the randomization) at visit 3 and will return for their final follow-up visit (visit 4) approximately 2-week after visit 3. Unscheduled follow-up visits may occur during the study. Subjects will be advised to wear the study lenses at least five (5) days per week for at least six (6) hours per day for a period of two-weeks each.

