5.2. Secondary Hypotheses

1. The Test lens will be non-inferior to the Control lens with respect to CLUE Overall quality of vision at the two-week follow-up evaluation. A non-inferiority margin of -5 points will be used.
2. The Test lens will be non-inferior to the Control with respect to CLUE Handling at the two-week follow-up evaluation. A non-inferiority margin of -5 points will be used.
3. The Test lens will be non-inferior the Control lens with respect to Overall quality of vision indoors at the 2-week follow-up evaluation. A non-inferiority cumulative odds ratio margin of 0.67 will be used.

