The non-inferiority odds ratio margin of 2 corresponds to no more than a 5% difference between the Test and Control lenses assuming the Control reference rate does not exceed 5%.

Individual Questionnaire Items

Overall quality of vision outdoors and vision satisfaction in bright lighting sample size estimates were calculated using historical data from [REDACTED]. One-thousand boot strap samples were simulated based on the historical data. For each replicated sample a generalized linear mixed model was used with a multinomial distribution and the cumulative logit as the link function. Lens wear sequence, lens type, period and first order carryover effect were included in the model as fixed effects. A variance component (VC) covariance structure was used to model the measurements between subjects across study periods.

The non-inferiority cumulative odds ratio margin of 0.67 corresponds to no more than a 10% difference between the Test and Control lenses assuming there is no difference between study lenses.

Table 11: Sample Size Estimates and Power Calculations for Primary Endpoints

Endpoint	Number per Subjects to Complete	Power
Distance Monocular Visual Acuity (logMAR)	4	80%
SLFs (Grade 3 or Higher)	50	80%
Acceptable lens Fit	65	80%
CLUE Comfort	30	87%
Vision Satisfaction in Bright Lighting	48	81%

Table 12: Sample Size Estimates and Power Calculations for Secondary Endpoints

Endpoint	Number per Subjects to Complete	Power
CLUE Handling	30	81%
CLUE Overall Quality of Vision	30	82%
Overall Quality of Vision Indoors	95	81%

As indicated in Table 11 and 12 above, the sample size chosen for this study was primarily driven by overall quality of vision indoors. The plan is to enroll 120 eligible subjects with a target of 105 subjects to complete the study. During the enrollment period, the subject drop-out rate will be closely monitored, if an unexpectedly high dropout rate is observed, then the targeted total enrollment number may be increased accordingly to ensure that a minimum of 105 subjects complete the study.

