Independent vague $N(0, 1000)$ priors for the regression coefficients β_i $i=1, \dots, 5$. For θ_n , we are considering the following priors

$$\begin{aligned}\pi_0(\theta_1) &\sim N(0, 100) \\ \pi_0(\theta_2 | \theta_1) &\sim N(0, 100) I(\theta > \theta_1) \\ \pi_0(\theta_3 | \theta_2) &\sim N(0, 100) I(\theta > \theta_2) \\ \pi_0(\theta_4 | \theta_3) &\sim N(0, 100) I(\theta > \theta_3)\end{aligned}$$

For the variance of random effects independent vague normal priors will also be used; $\sigma_p^2 \sim \text{inverse-gamma}(0.001, 0.001)$ and $\sigma_s^2 \sim \text{inverse-gamma}(0.001, 0.001)$. The Metropolis sample algorithm as implemented in the SAS/Stat MCMC Procedure will be used to estimate the posterior distributions of the unknown parameters. Inferences will be made based on the posterior credible interval for the relevant parameters.

Hypothesis Testing

The null and alternative hypotheses for superiority are as follows:

$$\begin{aligned}H_0 \quad OR &\leq 0.67 \\ H_A \quad OR &> 0.67\end{aligned}$$

Where OR represent the cumulative odds ratio of having higher rating of the Test lens compared to the Control lens. Non-inferiority will be declared if the lower bound of the 2-sided 95% credible confidence interval is above 0.67, i.e. $P(OR=e^{\beta_1} > 0.67 | y) = 0.975$.

Primary Safety Analysis:

Lens Fit Acceptance

Lens fit acceptance will be analyzed using a Bayesian Logistic regression random-effects model to estimate the proportion of subjects' eyes wearing the Test lens having acceptable lens fitting. The regression model will include period, sequence of lens wear and first order carryover effect as fixed effects. Site and subject will be included in the model as random effects.

Let $y_{ijklm}=1$ if an acceptable lens fit is observed for eyes wearing the Test lens only and $y_{ijklm}=0$ otherwise for the m^{th} subject, from the l^{th} site, for the i^{th} eye in the j^{th} period using the k^{th} sequence.

$$y_{ijklm} \sim \text{Binary} (p_{ijklm})$$

$$p_{ijklm} = \frac{\exp(\mu_{ijklm})}{1 + \exp(\mu_{ijklm})}$$

$$\mu_{ijklm} = \beta_0 + \beta_1 \text{Lens}_{i[j,k]} + \beta_3 \text{period}_{j1} + \beta_4 \text{period}_{j2} + \beta_5 \text{sequence}_k + \beta_6 \text{Carry1}_{i[j,k]} + \gamma_1 + \delta_{m(l)} + \alpha_{j(m(l))}$$

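### The 95 completers and 81% power for vision indoors cannot be reproduced from the SAP's printed counts, and the bright-light row (48, 81%) was not updated when its counts changed

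*SAP*

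**What the plan says.** SAP 8.4 sizes two ordinal questionnaire items by resampling: "One-thousand boot strap samples were simulated based on the historical data". On the model used it says: "Lens wear sequence, lens type, period and first order carryover effect were included in the model as fixed effects". The paragraph that describes this method names the items as vision **outdoors** and bright-light satisfaction. SAP Table 12 reports the result for vision **indoors**: 95 completers, 81% power. Table 11 gives bright light 48 completers, 81%.

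The closing text of SAP 8.4 states that "the sample size chosen for this study was primarily driven by overall quality of vision indoors", and Protocol 14.2 says the same ("the sample size chosen for this study was primary driven by overall quality of vision indoors"). The plan is 120 enrolled and 105 completers.

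For vision indoors, SAP 5.2 sets the criterion: "A non-inferiority cumulative odds ratio margin of 0.67 will be used". The decision rule in SAP 11.1, which SAP 11.2 applies to the indoors item, is: "Non-inferiority will be declared if the lower bound of the 2-sided 95% credible confidence interval is above 0.67".

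The historical counts are in Protocol Table 9 and SAP Table 10. The indoors counts are the same in both. The bright-light counts differ, yet Protocol Table 10 and SAP Table 11 both print 48 and 81% for that item.

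**The concern.** The row said to set the sample size ought to follow from the data printed beside it. On those data 95 completers look like far more than 81% power requires. The bright-light row has a more direct problem: its inputs were replaced and its output was not.

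Two things are at stake. If the indoors row needs only about 55 completers, the largest requirement in Tables 11 and 12 would be lens fit (65), and the stated rationale for the sample size would have to change. Also, neither row states the true odds ratio assumed. For visual acuity and slit lamp findings SAP 8.4 says openly that no difference was assumed, but for these two items the reader must infer that the historical Test advantage is expected to recur. Bright light is a primary endpoint, and SAP 5.1 requires every primary hypothesis to be met, so a failed non-inferiority test could not be interpreted without that information.

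**Working it through.** **1. The leftover cell.** In SAP Table 10 the Test column for bright light reads 65, 89, 24, 13, 0, which sums to 191. Three of its percentages use 181: 65/181 = 35.9%, 89/181 = 49.2%, 13/181 = 7.2%. The third cell, 24 (9.92), is 24/242, the entry in Protocol Table 9. A column total of 181 implies 14, and 14/181 = 7.7%.

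**2. Inputs.** From the documents: the printed counts; the margin 0.67 (ln 0.67 = -0.400); a 2-sided 95% interval (z = 1.96); sequences TCC and CTT (T = Test, C = Control); a model with sequence, period, lens and carryover. Not in the documents, so assumed: within-subject correlation (0 for the formula, latent 0.3 and 0.5 by simulation), and no historical sequence effect.

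**3. Formula.** A cumulative-logit fit to each pair of columns gives ln OR. The per-observation variance is Whitehead's approximation, s² = 3/(1 - Σp̄³), with p̄ the mean category proportions. With all four terms fitted in TCC/CTT, Var(ln OR) = 1.5 s²/N at zero correlation. Then

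- Power = Φ[(ln OR + 0.400)/√(1.5 s²/N) - 1.96]
- N for 81% = 1.5 s² (1.96 + 0.878)²/(ln OR + 0.400)²

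**4. Results at zero correlation.**

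| Counts | OR | ln OR | s² | N stated | Power at that N | N for 81% |
|---|---|---|---|---|---|---|
| Bright light, protocol | 1.68 | 0.521 | 3.62 | 48 | 78% | 52 |
| Bright light, SAP as printed (24) | 2.03 | 0.710 | 3.50 | 48 | 92% | 35 |
| Bright light, SAP with 14 | 2.39 | 0.873 | 3.54 | 48 | 97% | 27 |
| Indoors, both documents | 1.62 | 0.485 | 3.57 | 95 | 96% | 55 |

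The first row comes close to the plan's own 81%. For indoors: SE = √(1.5 × 3.57/95) = 0.237; (0.485 + 0.400)/0.237 = 3.73; Φ(3.73 - 1.96) = 0.96.

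**5. Simulation check** (400 trials per setting, same fixed effects, random subject intercept where correlation is above 0).

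- Indoors at 95: 96%, 97% and 99% at latent correlation 0, 0.3 and 0.5. At 45 completers and correlation 0.5: 85%.
- Bright light at 48, protocol counts: 80%, 86% and 91% at correlation 0, 0.3 and 0.5.
- Bright light at 48, SAP counts with 14: 96% at correlation 0 and over 99% at 0.3.

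In these checks positive correlation raised power at the historical odds ratio, so the missing correlation does not bring the indoors figure down to 81%.

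**6. What could bring it down.** In TCC/CTT the Test and Control observations are balanced over periods and over preceding lens, so period and carryover effects cancel in the pooled comparison. A sequence effect does not. Writing τ for the adjusted lens effect and σ for the effect of sequence TCC, the pooled log odds ratio is approximately τ - σ/3. At zero correlation, 81% at N = 95 needs τ = (1.96 + 0.878) × 0.237 - 0.400 = 0.273, an odds ratio of 1.31. Hence σ = 3 × (0.273 - 0.485) = -0.64. If the 363 indoors responses come from 121 subjects over three periods (363 = 3 × 121, an inference), the standard error of σ is √(1.5 × 3.57/121) = 0.21, so such an effect would lie about 3 standard errors from zero.

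**7. Equal lenses (OR = 1, zero correlation).** Indoors: 39% at 95 and 43% at 105, with about 269 completers needed for 81%. Bright light at 105: 42% on the protocol counts, 43% on the SAP counts. Assuming no difference therefore does not reproduce 81% at 95 either.

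**The case against.** The strongest reply is that the printed counts were not the input to the calculation. The power came from resampling subject-level records, and the documents print only marginal counts. As step 6 shows, a historical sequence effect of about -0.64 on the log-odds scale would give 81% at 95. It would be large, but it is not excluded. The method paragraph also names vision outdoors, which is a listed secondary endpoint (SAP 4.2) with no printed counts. Against that, the opening of SAP 8.4 lists indoors as powered, and Table 10 prints indoors counts. The documents do not settle which item the 95 refers to.

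A reader might therefore infer that the stated driver is not the driver, or that the bootstrap was run wrongly. The documents support neither inference. They support only that the figure cannot be reproduced from what is printed.

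Two further limits stand. The agreement of the protocol's bright-light counts with 48 and 81% holds only at low within-subject correlation; at 0.5 the same counts give 91%. And power at OR = 1 is a sensitivity request, not the correction of an error: the plan says it used historical data and prints the Test advantage.

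The reply does not reach the leftover cell, or the unchanged 48 and 81% beside changed counts.

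**Conclusion.** The point holds as a failure to reproduce and to update.

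- **Vision indoors.** The printed counts give about 96% power or more at 95 completers against 81% stated, and about 55 or fewer completers for 81%. This rests on no historical sequence effect and non-negative within-subject correlation. Whether the original run was sound, and whether it concerned indoors or outdoors, cannot be decided from the documents.
- **Bright light.** The row was kept although its counts were replaced. At 48 the SAP counts give about 92% as printed or 97% with the cell corrected, at zero correlation.
- **The cell 24 (9.92)** is a leftover from the protocol table.

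Under the historical advantage both items have more power than stated. If the lenses are in truth equal, both have about 42-43% at 105 completers (zero correlation). No margin, model or decision rule is affected.

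**What to change.** In SAP 8.4:

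1. State whether vision indoors or vision outdoors was sized, and make the method paragraph, Table 12 and the sentence on what drove the sample size agree.
2. Correct the cell 24 (9.92) in Table 10 against the source data; the other percentages imply 14 (7.7%).
3. Rerun the bootstrap on the final counts and restate the bright-light row of Table 11 and the vision row of Table 12, giving the adjusted odds ratio and subject variance assumed.
4. Amend the sentence on what drove the sample size if the rerun does not support it.
5. Add power at an odds ratio of 1 for both items at 105 completers as a sensitivity figure.

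The cost is one rerun of an existing simulation and a few lines of SAP text. Enrolment stays at 120, with 105 completers.
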